### 7.3 SCREENING

Participating study sites are required to document all screened subjects. If a subject is excluded from the study, the reasons for exclusion will be documented in the subject's source documents and noted on the Screening and Enrollment Log. All screening activities that occur prior to consent shall be referred to as pre-screening.

Part of the screening process will include documentation of women's childbearing potential. If the woman is not of child bearing potential this should be documented in the medical history (e.g. surgically postmenopausal, postmenopausal [i.e. at least 1 year without menses]). For women of childbearing potential their method of birth control should be documented in the source.

#### **7.4 INFORMED CONSENT**

Before conducting any study procedures or examinations, the purpose and nature of the study will be explained to the subject in their native language. Informed Consent Forms (ICF) requiring translation from English to a subject's native language will be translated by a certified third party vendor of the Sponsor's choosing. The translated ICF will then be submitted to the site's Institutional Review Board (IRB) for review and approval prior to distributing to potential subjects. The subject will then **read, sign, and personally date** the IRB -approved informed consent document(s) (see below for difficulties with reading and writing). Additionally, the individual who obtains consent from the subject will sign and date the informed consent document. A copy of the signed informed consent documentation will be provided to the subject and the original kept on site. Any additional requirements required by the IRB will be followed. If the subject is unable to read, the informed consent document and associated study information may be read aloud to the subject in the presence of an impartial witness. If possible the subject shall sign and personally date the Informed Consent Form. Where this is not possible, due to difficulties in writing, the subject shall provide verbal consent to participate in the study. The witness shall then personally sign and date the ICF, attesting that the information was accurately explained and that the informed consent was freely given.

#### **7.5 ENROLLMENT**

Enrollment in this study shall occur once the subject has successfully completed the informed consent process and successfully completed the Operative Visit (Day 1). A subject number will be assigned at the time of the Screening visit.

#### **7.6 LOST TO FOLLOW-UP**

Some actively enrolled subjects will not return for follow-up exams on time. Study personnel must make a reasonable effort to contact the subject and document the following contact attempts prior to declaring a subject to be lost to follow-up: the subject has been contacted according to the site's policies, but no fewer than 2 documented phone contacts and 1 certified

#### **CONFIDENTIAL AND PROPRIETARY**

This document contains information that is confidential and proprietary to Smith & Nephew PLC and Smith & Nephew, Inc. and is intended for use only by Smith & Nephew and its manufacturer. It shall not be reproduced or copied in whole or in part, nor shall the contents be disclosed by any means without prior written permission from Smith & Nephew, nor shall anyone make any use of it that is contrary to the expressed or implied wishes of Smith & Nephew.

Study Protocol—Device	
A Multicenter, Post Market, Prospective Study Evaluating Safety and Efficacy of CONQUEST FN™ for the Treatment of Intracapsular Femoral Neck Fractures	Number: 18-3047-02
	Version: 2.0, 30Nov2018
	Page: Page 21 of 63

letter without response. Copies of all attempts to reach the subjects per regular mail or email and/or the attempts to contact the subject via other means should be documented and that documentation should be kept with the subject's source documents.

## 7.7 WITHDRAWAL

### 7.7.1 Withdrawal from Study

The Investigator **may** withdraw subjects from the study for many reasons, including, but not limited to, the following:

- subject noncompliance (e.g. did not follow instructions, took disallowed medications)
- subject lost to follow-up
- if the Investigator or the Sponsor stops the study for any reason and decides to withdraw subject(s) from the study
- concurrent illness
- Adverse Events/Adverse Device Effects
- any other significant reason identified by the Investigator
- in the event any component of the original hardware is revised/exchanged

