### **7.7.3 Use of Data Following Withdrawal**

In cases where the subject withdraws consent, the data collected up to the point of withdrawal may be used but no additional data for that subject may be collected.

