#### **9.1.8 Discontinued Subjects**

Discontinued subjects are those who voluntarily discontinue participation, who are withdrawn for reasons of safety or use of prohibited concomitant treatments, or who are lost to follow-up.

Refer to section 7.8 for further details. Where possible, a full Exit Visit should be completed for all subjects who discontinue the study early. Where consent is withdrawn, the date and any reason given for discontinuation should be captured, at a minimum (see Section 7.7.1).

Any changes to medical health and/or the use of concomitant medications will be captured. If any SAE, SADE, or DevD were observed since the previous visit, they must be recorded (refer to section 11, Adverse Events and Device Deficiencies, for instructions on reporting and evaluation procedures). Finally, if appropriate, the Investigator will also advise the subject of subsequent therapy and/or procedures necessary for their medical condition.

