#### CONFIDENTIAL AND PROPRIETARY

This document contains information that is confidential and proprietary to Smith & Nephew PLC and Smith & Nephew, Inc. and is intended for use only by Smith & Nephew and its manufacturer. It shall not be reproduced or copied in whole or in part, nor shall the contents be disclosed by any means without prior written permission from Smith & Nephew, nor shall anyone make any use of it that is contrary to the expressed or implied wishes of Smith & Nephew.

Study Protocol—Device	
A Multicenter, Post Market, Prospective Study Evaluating Safety and Efficacy of CONQUEST FN™ for the Treatment of Intracapsular Femoral Neck Fractures	Number: 18-3047-02 Version: 2.0, 30Nov2018 Page: Page 37 of 63

**Not Related** - An AE is considered to be not related to the use of a study device or the procedure when the effect is DEFINITELY UNRELATED or UNLIKELY to have any relationship to the use of the study device or the procedure;

**Related** – An AE is considered to be related to the use of a study device or the procedure when there is a POSSIBLE, PROBABLE, or DEFINITE relationship between the AE and the use of the study device or the procedure.

An ADE is further categorized depending on whether the criteria in section 12.1.3 and 12.1.4 are met.

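### Section 7.7.1 lets the Investigator withdraw implanted subjects for noncompliance, concurrent illness or adverse events, and nothing requires their re-operation status to month 12

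*Combined protocol and SAP*

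**What the plan says.** Section 7.7.1 gives the Investigator a permissive, open-ended power to "withdraw subjects from the study for many reasons, including, but not limited to, the following". Besides noncompliance, the list includes "concurrent illness" and "Adverse Events/Adverse Device Effects". It has a separate entry for "subject lost to follow-up", which section 7.6 handles with its own contact rules. The primary endpoint (8.3.1) is re-operation for any reason at one year, and 9.4.1 reports it as a proportion with a two-sided confidence interval.

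Several sections bear on what happens after such a withdrawal:

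- Section 9.1.8, Discontinued Subjects: "Where possible, a full Exit Visit should be completed for all subjects who discontinue the study early". Serious events and device deficiencies since the previous visit are also to be recorded.
- Section 11.1.2: an event counts as related "when there is a POSSIBLE, PROBABLE, or DEFINITE relationship between the AE and the use of the study device or the procedure".
- Section 11.3.1: related events still ongoing at exit are followed until resolved or chronic; unrelated ones for at most 30 days.
- Section 11.2: updates to submitted event information go into the CRF within 24 hours.
- Section 11.3: the Sponsor decides whether additional data enter the CRF.
- Section 17: reasonable efforts are to be made to keep subjects to 12 months.
- Section 7.7.3: where consent is withdrawn, "the data collected up to the point of withdrawal may be used but no additional data for that subject may be collected".
- Section 9.3: an accountability report will explain withdrawals.
- Section 7.7.1, Replacement Policy: enrolled subjects who drop out are not replaced.

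**The concern.** In a drug trial, withdrawal for an adverse event or noncompliance may at least stop a treatment. Here the implant is already in place, so what ends is observation. A subject withdrawn at month 3 can still be re-operated at month 8, and no section obliges the site to find out. Status that was never collected cannot be recovered by the SAP, which section 9 says is still to be written.

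At stake is the primary rate in each fracture group. It is too low if withdrawn subjects carry a higher risk and their later re-operations go unseen. It is too high if they carry a lower risk and leave the denominator, or if their early re-operations are counted while event-free withdrawn subjects drop out.

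**Working it through.** **Inputs from section 10.** 90 enrolled for 80 evaluable; 45 per fracture group; assumed success 87% (displaced) and 93% (non-displaced), so re-operation rates p of 13% and 7%; precision within 12% and 10%; loss to follow-up 5%.

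**The plan's own figures.** With 80/2 = 40 evaluable per group, the Wald half-width is 1.96 × √(0.87 × 0.13/40) = 10.4% for displaced and 1.96 × √(0.93 × 0.07/40) = 7.9% for non-displaced. Clopper-Pearson gives 11.5% and 9.2%. The stated 12% and 10% therefore hold. A 5% loss would need only 80/0.95 = 84.2, so 85 enrolled. Enrolling 90 for 80 allows 1 - 80/90 = 11.1% loss.

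**Assumptions.** The documents give no expected number of Investigator withdrawals and no risk for such subjects. Let w be the share withdrawn by these routes and RR their re-operation risk relative to retained subjects. Two values of w are used: 5%, borrowed from the loss-to-follow-up rate, and 1/9 (11.1%), the whole planned allowance.

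**Withdrawn subjects leave the denominator, none of their events seen.** The retained rate, which is what would be observed, is r = p/(1 + w(RR - 1)).

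| w | RR | Displaced (true 13%) | Non-displaced (true 7%) |
|---|---|---|---|
| 5% | 0 | 13/0.95 = 13.68 (+0.68) | 7/0.95 = 7.37 (+0.37) |
| 5% | 0.5 | 13/0.975 = 13.33 (+0.33) | 7/0.975 = 7.18 (+0.18) |
| 5% | 2 | 13/1.05 = 12.38 (-0.62) | 7/1.05 = 6.67 (-0.33) |
| 5% | 3 | 13/1.10 = 11.82 (-1.18) | 7/1.10 = 6.36 (-0.64) |
| 11.1% | 3 | 13/1.222 = 10.64 (-2.36) | 7/1.222 = 5.73 (-1.27) |

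**Expected missed re-operations per 45, at RR 3: 45 × w × RR × r.**

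- w = 5%: 2.25 × 3 × 0.1182 = 0.80 (displaced); 2.25 × 3 × 0.0636 = 0.43 (non-displaced).
- w = 11.1%: 5 × 3 × 0.1064 = 1.6 (displaced); 5 × 3 × 0.0573 = 0.9 (non-displaced).

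**Half of the withdrawn subjects' events fall before withdrawal and are recorded; event-free withdrawn subjects leave the denominator (w = 5%).** With s = 0.5 × w × RR × r, the observed rate is [r(1 - w) + s]/[(1 - w) + s]. For displaced at RR 1 this is (0.1235 + 0.00325)/(0.95 + 0.00325) = 13.30%, a rise of 0.30. At RR 2 and 3 the shifts are -0.05 and -0.37. For non-displaced at RR 1, 2 and 3 they are +0.17, -0.01 and -0.17. The sign depends on when events fall as well as on the risk ratio.

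**Withdrawn subjects counted as non-events.** The observed rate is r(1 - w), and missed events can only lower it. At w = 5% and equal risk it is 13 × 0.95 = 12.35 (-0.65) and 7 × 0.95 = 6.65 (-0.35). Section 9.4.1 does not choose between this handling and the ones above.

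**Why none of these is a bound.** If 5 of 45 displaced subjects were withdrawn and every one was re-operated unseen, 6/45 = 13.3% would become 11/45 = 24.4%, a move of 11.1 points. Nothing suggests this would happen, but it shows that the small figures come from the assumed risk ratios.

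**The case against.** The strongest reply is that the gap is narrow and the effect immaterial. The clause is permissive. The exit visit under 9.1.8 should capture re-operations up to exit, and section 17 asks sites to retain subjects. The adverse-event route, the one that the Background (4.1) ties most directly to re-operation, is the best covered, because a possibly related event counts as related and is followed until resolved or chronic. Entry criteria screen out likely non-compliers. The disallowed-medication example of noncompliance has no content here, since 8.4.7.1.1 excludes no medication. No performance goal turns on the result. The contents of the End of Study CRF are not in the documents, so routine capture cannot be ruled out.

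Most of this stands and keeps the grading low. It does not close the gap. The exit visit is asked for where possible and is not tied to month 12. Section 11.3.1 follows an ongoing event, not re-operation status, and gives nothing for noncompliance without an event. Section 11.2 does not expressly address updates after withdrawal. The accountability report shows the loss without supplying the outcome. By contrast, section 7.6 requires two phone contacts and a certified letter before a subject is declared lost; no comparable effort is required for a reachable subject whom the Investigator withdraws.

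A reader might infer that these withdrawals flatter the device. The documents do not support a direction: they give no risk for withdrawn subjects, and the shift can go either way. A reader might also infer that 5% caps the loss, so that fewer than one re-operation per group could be missed. That 5% is a loss-to-follow-up rate, a separate entry in 7.7.1, and the enrolment figures allow 11.1%. Nor does the plan forbid further collection: 7.7.3 bars it only after consent is withdrawn.

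**Conclusion.** The concern holds as a cheap improvement, not as a demonstrated bias. Following 7.7.1 as written can lose primary-endpoint data that no later analysis can restore, and no section requires re-operation status to month 12 for subjects withdrawn for noncompliance, concurrent illness or adverse events. Cover is partial, and least for noncompliance and unrelated illness.

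If withdrawn subjects leave the denominator, 5% withdrawal and risk ratios of 0 to 3 shift the displaced rate by about +0.7 to -1.2 points and the non-displaced rate by about +0.4 to -0.6. If the full 11.1% came by these routes at three times the risk, the shifts are about -2.4 and -1.3 points, with about 1.6 and 0.9 missed re-operations per 45. Withdrawal share, risk ratio and handling are all assumed. These illustrative shifts are below the stated precision of 12% and 10%, and no decision rule depends on them. Withdrawal after hardware revision, and subjects lost under 7.6, are outside this point.

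**What to change.** Add to section 7.7.1: *Noncompliance, concurrent illness and AE/ADE are recorded but do not by themselves end follow-up for re-operation. Unless consent is withdrawn, re-operation status (date and reason) of subjects withdrawn by the Investigator for these reasons is obtained to 12 months, by phone or record review if visits stop, and entered in the CRF.* This is a data-collection rule only; clinical care stays with the Investigator.

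The cost is one amendment with IRB approval at about 10 sites, possibly a check of the consent wording (the consent pages are not in the reviewed text), and phone or record checks for about 5 subjects at 5% loss (0.05 × 90 = 4.5) or about 10 at 11.1% (90 - 80). It needs no extra patients or procedures. Section 14 reserves amendments for exceptional cases once the study has started, so after that point the change is best bundled with the next amendment.

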#### *Replacement Policy*

Subjects who dropout before being enrolled (i.e. during Screening) will be replaced. Subjects who drop out of the study after being enrolled, for whatever reason, will not be replaced. Any subject who drops out after randomization will not be permitted to re-enroll into the study at a later date.

For each case, information will be obtained in the source document and the End of Study Case Report Form (CRF), detailing circumstances leading to the withdrawal.

### 7.7.2 Subject's Withdrawal of Consent to Participate in Study

#### **CONFIDENTIAL AND PROPRIETARY**

This document contains information that is confidential and proprietary to Smith & Nephew PLC and Smith & Nephew, Inc. and is intended for use only by Smith & Nephew and its manufacturer. It shall not be reproduced or copied in whole or in part, nor shall the contents be disclosed by any means without prior written permission from Smith & Nephew, nor shall anyone make any use of it that is contrary to the expressed or implied wishes of Smith & Nephew.

Study Protocol—Device	
A Multicenter, Post Market, Prospective Study Evaluating Safety and Efficacy of CONQUEST FN™ for the Treatment of Intracapsular Femoral Neck Fractures	Number: 18-3047-02
	Version: 2.0, 30Nov2018
	Page: Page 22 of 63

Study participation is voluntary and subjects may withdraw at any point during the study without giving their reason for doing so. Where subjects withdraw consent, the Investigator should make a reasonable effort to ascertain the reason(s), while fully respecting the subject's privacy. The reason for withdrawal will be recorded in the CRF and in source documents.

### **7.7.3 Use of Data Following Withdrawal**

In cases where the subject withdraws consent, the data collected up to the point of withdrawal may be used but no additional data for that subject may be collected.

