#### **11.3.1 Ongoing Adverse Events at Study Discontinuation**

Adverse events which are **related** to a study procedure or S&N study device and are ongoing at end of subject's participation: The event should be followed until it is either resolved or until the event has become chronic and is not expected to further improve based on Investigator's review of the event.

Adverse events which are **not related** to a study procedure or S&N study device and are ongoing at end of subject's participation should be followed for 30 days after discontinuation or if the AE is resolved, whichever is sooner.

At the time of data analysis (e.g. interim or final), an evaluation of ongoing events should take place and be listed as ongoing in the safety table.

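### The protocol does not separate stopping study visits from withdrawing consent to all data, gives no route to one-year re-operation status after a subject leaves, and does not reconcile 7.7.3 with 11.3.1

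*Combined protocol and SAP*

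**What the plan says.** Section 7.7.2 gives an open right to leave: "Study participation is voluntary and subjects may withdraw at any point during the study without giving their reason for doing so". It then moves straight to withdrawn consent without saying whether the two are the same. Section 7.7.3 begins "In cases where the subject withdraws consent" and rules that "the data collected up to the point of withdrawal may be used but no additional data for that subject may be collected". Neither section describes a partial withdrawal.

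The section headed Discontinued Subjects (numbered 9.1.8, though it sits within Section 8.4) is wider. It starts "Discontinued subjects are those who voluntarily discontinue participation" and adds subjects withdrawn for safety or prohibited treatments and those lost to follow-up. Its general instruction is "Where possible, a full Exit Visit should be completed for all subjects who discontinue the study early". Withdrawn consent is handled apart: "Where consent is withdrawn, the date and any reason given for discontinuation should be captured, at a minimum".

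Section 11.3.1 deals with adverse events still open when participation ends. For those related to the device or a study procedure it says "The event should be followed until it is either resolved or until the event has become chronic and is not expected to further improve". Unrelated events are followed for 30 days, or until resolution if that comes sooner. Section 11.3 also recommends a follow-up visit after early discontinuation and wants further data documented and open to the sponsor. None of this text mentions withdrawn consent.

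The primary endpoint (8.3.1) is re-operation for any reason at one year. Section 9.4.1 reports it as a proportion with a two-sided confidence interval.

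**The concern.** The endpoint is a yes/no with a date. It does not need study films, questionnaires or function tests, and could be read from the hospital record or learned in one call. A subject who is tired of visits may be quite willing to allow that, but the protocol never asks.

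Two things are at stake. First, leaving the study is unlikely to be independent of how the hip is doing, and few events are expected, so each subject of unknown status carries weight. The planned interval covers sampling error only. Drop-outs after enrolment are not replaced (7.7.1), the full analysis set needs only one post-baseline assessment (9.2), and 9.4.1 does not say how to count a subject whose one-year status is unknown. Secondly, a site whose subject withdraws consent with an adverse event open has one section telling it to collect nothing and another telling it to follow the event.

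**Working it through.** **1. Ways out of the study, side by side**

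| Route | Where | At exit | Re-operation status to one year |
|---|---|---|---|
| Voluntary discontinuation, consent not withdrawn | 9.1.8 | Full Exit Visit where possible | No provision |
| Consent withdrawn | 7.7.2, 7.7.3, 9.1.8 | Date and any reason; earlier data kept | Barred |

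The Exit Visit takes place on leaving, so it captures events up to that day only. The one later contact in the plan is follow-up of an event already open (11.3, 11.3.1), which is not a check of re-operation status and does not reach subjects with no open event.

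Nothing tells a site how to place a subject in one row or the other. The cross-references do not help: 9.1.8 points to a Section 7.8, but the contents list ends Section 7 at 7.7, and for withdrawn consent it points to 7.7.1 although that topic is in 7.7.2.

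**2. Section 7.7.3 against 11.3.1**

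For a subject who leaves with consent intact, 11.3.1 applies and 7.7.3 does not, so there is no clash. For a subject who withdraws consent with an event open, both apply by their wording: 7.7.3 stops collection, while 11.3.1 expects follow-up, of related and unrelated events alike, with no exception. No section ranks them.

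**3. The plan's own figures**

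Section 10 gives 45 per fracture type, assumed success of 87% (displaced) and 93% (non-displaced), margins of 12 and 10 points, 5% loss, and 90 enrolled for 80 evaluable.

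- Loss: 80/(1 − 0.05) = 84.2, so 85 would suffice. Going from 90 to 80 allows for 10/90 = 11.1% loss. The 90 is not reproduced at 5%, but it errs on the safe side; this is a separate matter.
- Precision: the Clopper-Pearson half-width at 40 per group is 11.5 points (displaced) and 9.2 points (non-displaced), so the stated margins hold as upper limits.

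**4. Illustration of unknown status**

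Expected re-operations: 45 × 0.13 = 5.85, about 6; 45 × 0.07 = 3.15, about 3. If m of 45 subjects have unknown status, the gap between none and all of them being re-operated is m/45:

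| m (assumed) | Gap, points |
|---|---|
| 1 | 2.2 |
| 2 | 4.4 |
| 3 | 6.7 |
| 5 | 11.1 |

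For m = 2, close to the whole 5% allowance (0.05 × 45 = 2.25):

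- Displaced: 6/45 = 13.3% to (6 + 2)/45 = 17.8%; known cases only, 6/43 = 14.0%.
- Non-displaced: 3/45 = 6.7% to (3 + 2)/45 = 11.1%; known cases only, 3/43 = 7.0%.

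For the overall rate, each unknown subject moves the bound by 1/90 = 1.1 points.

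**The case against.** A reader might infer that 7.7.3 turns every early exit into a ban on data. It does not: its opening words limit it to withdrawn consent, and 9.1.8 recognises voluntary discontinuation separately, with an Exit Visit. No section tells a site to record a wish to stop visits as withdrawn consent. That stands. What remains is that the two are not told apart, and that neither route leads to one-year status.

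A reader might also infer that 11.3.1 demands follow-up to resolution and so flatly contradicts 7.7.3. It says should, it also stops at a chronic event not expected to improve, and 11.3 only recommends the visit. One can fairly read 7.7.3 as the specific rule and 11.3.1 as the general one. The gap is one of scope and a missing cross-reference, but the protocol does not say which reading is meant.

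Nor does the date-and-reason minimum in 9.1.8 conflict with 7.7.3. It documents the withdrawal itself, in line with 7.7.2, and does not ask for later outcomes.

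A ban after full withdrawal of consent respects the subject's decision and is not a defect. The consent form was not available for this review and may already offer a limited option. Section 17 asks for reasonable efforts to retain subjects to 12 months, Section 9.3 promises an account of withdrawn subjects, and Section 9 leaves detail to a SAP still to be written. These help, but a SAP cannot recover a status that nobody was permitted to collect.

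Finally, the upper bounds need every unknown subject to be re-operated after leaving; re-operations recorded earlier are kept. Two consent withdrawals per group would use almost all of the 5% allowance. This is correct, so the figures are bounds and not expected bias.

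**Conclusion.** The point holds as a gap in the withdrawal rules that is cheap to close; it is not an error in the planned statistics. Sections 7.7.2 and 7.7.3 do not separate stopping visits from refusing all further data, no section provides for re-operation status after exit, and 11.3.1 is unreconciled with 7.7.3 where consent is withdrawn with an event open.

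The size is up to 2.2 points per subject of unknown status in a group of 45, a worst-case bound that the confidence interval does not cover. The precision slack in Section 10 does not answer this, because it concerns sampling error and not selective loss. The number withdrawing consent is an assumption, since the plan gives only a 5% total loss, and the share who would allow a status check is unknown.

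**What to change.** In 7.7.2 and 7.7.3, and in the consent form if it is not already there, offer two options at withdrawal:

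- (a) stop study visits, but allow re-operation status and date to Day 365, and the outcome of open adverse events, to be taken from medical records or one call;
- (b) withdraw fully, with no further data.

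Limit the ban in 7.7.3 to (b). Cross-reference 9.1.8 and 11.3.1 so that the passages are reconciled, and record the option chosen on the End of Study CRF. The change concerns data collection only, not the care a subject receives.

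Cost: one paragraph in the protocol and consent form, one CRF field, IRB approval, and one record check or call for each subject who chooses (a). Only those subjects' outcomes are recovered. Subjects choosing (b) will still have unknown status, so the SAP should say how they are counted.
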